7.1.5.2. Incomplete Dates

If the onset date of the AE is incomplete and the AE stop date is not prior to the first dosing date of study drug, then the month and year (or year alone if month is not recorded) of onset determine whether an AE is treatment emergent. The event is considered treatment emergent if both of the following 2 criteria are met:

- The AE onset is the same as or after the month and year (or year) of the first dosing date of study drug, and
- The AE onset date is the same as or before the month and year (or year) of the date corresponding to 30 days after the date of the last dose of study drug

An AE with completely missing onset and stop dates, or with the onset date missing and a stop date later than the first dosing date of study drug, will be considered to be treatment emergent. In addition, an AE with the onset date missing and incomplete stop date with the same or later month and year (or year alone if month is not recorded) as the first dosing date of study drug will be considered treatment emergent.

In case when the AE onset date is incomplete and needs to be imputed, the following algorithm will be followed:

- If the day is missing but the month and year are available, then the imputed day will be the first day of the month or the first dosing date if they have the same month and year, whichever is later.
- If the day and month are missing but year is available, then the imputed day and month will be 01Jan or the first dosing date if they have the same year, whichever is later.

7.1.6. Summaries of Adverse Events and Deaths

Treatment-emergent AEs will be summarized based on the Safety Analysis Set.

7.1.6.1. Summaries of AE Incidence by Severity

The number and percentage of subjects who experienced at least 1 TEAE will be provided and summarized by SOC, HLT, PT, and treatment group. For the AE categories described below, summaries will be provided by SOC, PT, maximum severity, and treatment group:

- TEAEs
- TEAEs with Grade 3 or higher
- TEAEs related to tirabrutinib
- TEAEs related to idelalisib
- TEAEs related to obinutuzumab

- TEAEs related to tirabrutinib with Grade 3 or higher
- TEAEs related to idelalisib with Grade 3 or higher
- TEAEs related to obinutuzumab with Grade 3 or higher
- TE SAEs
- TE SAEs related to tirabrutinib
- TE SAEs related to idelalisib
- TE SAEs related to obinutuzumab
- TEAEs leading to discontinuation of tirabrutinib
- TEAEs leading to discontinuation of idelalisib
- TEAEs leading to discontinuation of obinutuzumab
- TEAEs leading to dose modification of tirabrutinib
- TEAEs leading to dose modification of idelalisib
- TEAEs leading to dose modification of obinutuzumab
- TEAEs leading to temporary interruption of tirabrutinib
- TEAEs leading to temporary interruption of idelalisib
- TEAEs leading to temporary interruption of obinutuzumab
- TEAEs leading to discontinuation of study
- TEAEs leading to death (note that the severity will not be shown as all the TEAEs are Grade 5)

A brief, high-level summary of AEs described above will be provided by treatment group and by the number and percentage of subjects who experienced the above AEs. This summary table will also include TEAEs with Grade 3 or 4 and all deaths.

Multiple events will be counted only once per subject in each summary. Adverse events will be summarized and listed first in alphabetic order of SOC and then by PT in descending order of total frequency within each SOC. For summaries by severity, the most severe severity will be used for those AEs that occurred more than once in a given subject during the study.

In addition to the above summary tables, TEAEs, TEAEs of Grade 3 or higher, TE treatment-related AEs, and TE SAEs will be summarized by PT only in descending order of total frequency.

In addition, data listings will be provided for the following:

- All AEs, indicating whether the event is treatment emergent
- All AEs with Grade 3 or higher
- All SAEs
- All Deaths
- AEs leading to death
- AEs leading to discontinuation of study drug
- AEs leading to discontinuation of study

7.1.6.1.1. Summary of Deaths

A summary (number and percentage of subjects) of deaths will be provided by treatment group. The summary will include the following categories:

- All deaths
- Deaths within 30 days of the last dosing of study drug
- Deaths beyond 30 days of the last dosing of study drug

The attribution of death will also be summarized.

7.1.7. Adverse Events of Interest

The treatment-emergent AEs of interest (AEI) include:

AEI	Grouped Terms
Hemorrhage/Bleeding	MST-CT Bleeding/Haemorrhage (Appendix 4)
Infections	SOC: Infections and infestations
Hypersensitivity	MST-CT Hypersensitivity (Appendix 5)
Cytopenia	MST: Anemia-related events, leukopenias, neutropenia, thrombocytopenias (Appendix 6)
Cardiac Arrhythmias	MST-CT Cardiac arrhythmia and bradycardia_narrow (Appendix 7)
Diarrhoea	PT: Diarrhoea
Rash	MST-CT Rash - specific to ONC (Appendix 8)

The following summaries will be provided for AEs by SOC, PT, and maximum severity:

- A) TEAE
- B) TEAEs leading to dose modifications or temporary interruption of study drug
- C) TEAEs leading to discontinuation of study drug

A data listing of AEs will be provided by alphabetic ascending order of AE name, then by subject ID.

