1.3.4. Clinical Trials of Tirabrutinib

Tirabrutinib is an orally administered, potent and selective inhibitor of BTK initially evaluated in a Phase 1 single agent dose escalation study, ONO-4059POE001, conducted in the United Kingdom (UK) and France {Walter 2015}. This study enrolled and treated 90 subjects with relapsed CLL, non-GCB DLBCL, MCL, SLL, and other indolent non-Hodgkin's lymphomas (iNHLs). Tolerability and efficacy of tirabrutinib monotherapy have been demonstrated in subjects with CLL at doses ranging from 20 to 600 mg once daily with no maximum tolerated dose (MTD) identified. Responses were observed in subjects in the NHL cohort at doses from 40 to 480 mg. Dose limiting toxicities (DLTs) of rash and non-immune reaction were observed at 600 mg once daily in the NHL cohort. For CLL patients, the most common AEs were contusion, neutropenia, anemia, and nasopharyngitis and the most frequent AEs attributed to tirabrutinib were hematoma, macule, dry skin, neutropenia, pruritus, diarrhea, and contusion. The most frequent \geq Grade 3 AEs were neutropenia, anemia, thrombocytopenia, and lower respiratory tract infection.

All subjects continuing on tirabrutinib treatment have been transitioned to the GS-US-401-1787 continuation study; as of 01 June 2016, 27 subjects (18 with CLL) are continuing on treatment with tirabrutinib at doses ranging from 80 to 600 mg once daily with a median duration on study of 799 days.

Study ONO-4059-01 is an ongoing open-label, multi-center, non-randomized Phase 1 dose-escalation study of tirabrutinib monotherapy in Japanese subjects with relapsed/refractory B-NHL and CLL. This study utilizes a 3+3 design with dose levels ranging from 160 to 600 mg daily. As of 05 May 2016, 17 subjects had enrolled. The only AEs attributable to study drug were Mallory-Weiss syndrome (1), HBV reactivation (1), and pneumonitis (1; subject had pre-existing organizing pneumonia). All subjects resumed treatment with lower doses of study drug. Rash, anemia, lymphopenia, hypophosphatemia, hypokalemia and emesis were the only AEs reported in more than 1 subject (n = 2 for all except n = 5 for rash).

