Appendix 6. Cytopenia Medical Search Term

Note: The list presented below is based on MedDRA Version 22.0. The actual list will be up-versioned to the MedDRA version used at the time of database finalization.

MEDDRA Preferred Term	PT Code
Acquired amegakaryocytic thrombocytopenia	10076747
Megakaryocytes decreased	10027119
Mononuclear cell count decreased	10082036
Platelet count decreased	10035528
Platelet maturation arrest	10035537
Platelet production decreased	10035540
Platelet toxicity	10059440
Thrombocytopenia	10043554
Febrile neutropenia	10016288
Neutropenia	10029354
Neutrophil count decreased	10029366
Agranulocytosis	10001507
Autoimmune neutropenia	10055128
Transfusion-related alloimmune neutropenia	10081503
Granulocytopenia	10018687
Idiopathic neutropenia	10051645
Neutropenic colitis	10062959
Neutropenic infection	10059482
Neutropenic sepsis	10049151
Neutrophil count abnormal	10061313
Band neutrophil count decreased	10057950
Band neutrophil percentage decreased	10059130
Neutrophil percentage abnormal	10058134
Neutrophil percentage decreased	10052223
Granulocyte count decreased	10018681
Granulocytes abnormal	10018685
Anaemia macrocytic	10002064
Aplasia pure red cell	10002965
Aplastic anaemia	10002967
Erythroblast count decreased	10058505

MEDDRA Preferred Term	PT Code
Erythroid maturation arrest	10015279
Erythropenia	10015287
Hypoplastic anaemia	10021074
Microcytic anaemia	10027538
Proerythroblast count decreased	10060229
Red blood cell count decreased	10038153
Reticulocyte count decreased	10038790
Reticulocytopenia	10038795
Anaemia	10002034
Anaemia neonatal	10002068
Erythroblast count abnormal	10058508
Erythropoiesis abnormal	10049467
Foetal anaemia	10077577
Haematocrit abnormal	10049221
Haematocrit decreased	10018838
Haemoglobin abnormal	10018879
Haemoglobin decreased	10018884
Leukoerythroblastic anaemia	10053199
Normochromic anaemia	10029782
Normochromic normocytic anaemia	10029783
Normocytic anaemia	10029784
Proerythroblast count abnormal	10060227
Red blood cell count abnormal	10038151
Reticulocyte count abnormal	10038788
Reticulocyte percentage decreased	10059921
Autoimmune aplastic anaemia	10071576
Bicytopenia	10058956
Bone marrow failure	10065553
Cytopenia	10066274
Febrile bone marrow aplasia	10053213
Full blood count decreased	10017413

MEDDRA Preferred Term	PT Code
Gelatinous transformation of the bone marrow	10078097
Pancytopenia	10033661
Panmyelopathy	10050026

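### The Cytopenia AE-of-interest definition in SAP 7.1.7 includes leukopenias, but SAP Appendix 6 lists no total-white-cell or lymphocyte term, so events coded to such terms fall outside that grouping

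*SAP*

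**What the plan says.** The table in SAP 7.1.7 defines the Cytopenia AEI as "MST: Anemia-related events, leukopenias, neutropenia, thrombocytopenias" and refers to SAP Appendix 6 for the terms. Leukopenias and neutropenia are named as separate groups. For each AEI the section plans three summaries by system organ class, preferred term and maximum severity: treatment-emergent events, those leading to dose modification or interruption, and those leading to discontinuation of study drug.

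SAP Appendix 6 is the working list of preferred terms. Its note gives one way in which the list will change: "The actual list will be up-versioned to the MedDRA version used at the time of database finalization". SAP section 1 adds that changes made after the SAP is final will be documented in the study report.

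**The concern.** The label and the list do not match. A programmer will build the grouping from Appendix 6, while a reader of the report will take its content from 7.1.7. An event coded to Leukopenia or White blood cell count decreased belongs in the group by the definition but would not be flagged by the list. Up-versioning to a later dictionary release would not supply a missing group of terms.

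Such events can reach the adverse event database. Protocol 7.1.3 requires a laboratory abnormality to be recorded as an adverse event if it needs intervention or leads to interruption, modification or discontinuation of study drug. Two of the three planned AEI summaries are restricted to events with consequences of that kind. At stake is whether the reported cytopenia frequency, overall and in those two summaries, covers what its definition says it covers.

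**Working it through.** The plan gives no figure to reproduce here. The check compares the definition with the list.

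**Step 1: sort the list.** SAP Appendix 6 prints 64 preferred terms:

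| Cell line | Terms |
|---|---|
| Platelet/megakaryocyte | 7 |
| Neutrophil/granulocyte | 18 |
| Red cell | 29 |
| Multilineage/marrow | 9 |
| Mononuclear | 1 |
| Total | 7 + 18 + 29 + 9 + 1 = 64 |

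**Step 2: search for white-cell terms.**
- The stem leuk gives one match, "Leukoerythroblastic anaemia", which is an anaemia term.
- The stems lymph, white, wbc, monocyt, eosin and basoph give none.
- The stem mononuc gives one match, "Mononuclear cell count decreased", printed among the platelet terms.

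**Step 3: compare with the definition.**

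| Group named in SAP 7.1.7 | Terms in SAP Appendix 6 |
|---|---|
| Anemia-related events | 29 red-cell terms |
| Neutropenia | 18 terms, for example "Granulocyte count decreased" |
| Thrombocytopenias | 7 terms |
| Leukopenias | No total-white-cell term and no lymphocyte term; one mononuclear term |

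The 9 multilineage terms (Pancytopenia, Cytopenia and similar) capture a low white count only when the event is coded as failure of more than one line.

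**Step 4: where the omitted events would still appear.** SAP 7.1.6.1 tabulates all treatment-emergent events by class and preferred term, with separate tables for Grade 3 or higher, serious, related, discontinuation, dose-modification and interruption events, and lists all events. SAP Appendix 9 includes white cells and lymphocytes among the laboratory tests, which are summarized by grade (7.2.2.2) and in shift tables (7.2.4). The loss is therefore confined to the AEI grouping. The general tables do not restore a grouped frequency, because adding preferred-term rows would count some subjects more than once.

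**Step 5: size.** About 30 subjects are planned for Arm B. One subject missing from the group changes a subject-level cytopenia percentage by 1/30 = 3.3 points. This is a maximum: SAP 7.1.6.1 counts a subject once per summary, so a subject who also has a listed neutropenia, anaemia or thrombocytopenia event is already in the group and the change is 0. The range per affected subject is 0 to 3.3 points.

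**The case against.** **The events are counted elsewhere.** This stands. A reader might infer from the gap that leukopenia events will go uncounted in the study. The documents do not support that, as step 4 shows.

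**The list does contain white-cell terms.** This also stands. Neutrophil, granulocyte and mononuclear terms are present, so it would be wrong to say that the list has no term for a decrease in white cells. One could argue that the granulocyte terms fill the leukopenias group. But 7.1.7 names neutropenia separately, so leukopenias should add something to it, and one mononuclear term is a thin addition in a list broad enough to include foetal anaemia.

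**Lymphopenia may be left out on purpose.** This is a fair argument. SAP 7.1.7 never names lymphopenia, and the source search term is not in the documents. A falling lymphocyte count is part of response in CLL: the response criteria in Protocol Appendix 6 require lymphocytes below 4000/µL for complete remission and a decrease of at least 50% for partial response. The absence of lymphocyte terms is therefore a question to settle, not an established omission. The argument does not explain the absence of total-white-cell terms.

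**The evidence that such events are frequent is weak.** Protocol 1.3.4 says of the Japanese tirabrutinib study that "Rash, anemia, lymphopenia, hypophosphatemia, hypokalemia and emesis were the only AEs reported in more than 1 subject". Lymphopenia was seen in 2 subjects, or 2/17 = 12% of those enrolled, and a reader might carry that figure over to this trial. It does not transfer. That study gave monotherapy at 160 to 600 mg daily in B-cell lymphoma and CLL, and lymphopenia was not among the events attributed to the drug. Closer evidence gives no support either. Neither leukopenia nor lymphopenia appears among the events above 10% in the 23 subjects given tirabrutinib with idelalisib (Protocol 1.3.4), or above 15% in the 32 given idelalisib with obinutuzumab (Protocol 1.4).

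**Conclusion.** The mismatch is real and minor. Followed as written, the plan leaves events coded to a total-white-cell or lymphocyte term out of the Cytopenia AEI. For total-white-cell terms, that contradicts the definition in 7.1.7. For lymphocyte terms, the documents do not settle whether inclusion was intended.

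The understatement is at most 3.3 points per affected Arm B subject, and only for a subject with no other listed cytopenia event. How many subjects would be affected cannot be estimated from the documents. The figure assumes 30 treated subjects in Arm B and a pooled row for any cytopenia; 7.1.7 specifies summaries by class and preferred term and does not explicitly promise such a row. The grouping is descriptive, and the primary endpoint does not use it.

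The finding also assumes that the list as read is complete. Its blocks follow one another without a visible gap or redaction, so loss of terms in text extraction is unlikely, but it cannot be fully excluded.

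**What to change.** Before database finalization:

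1. Check SAP Appendix 6 against the source leukopenia search term.
2. Either add the missing leukopenia and white-cell-decreased preferred terms, or remove leukopenias from the definition in SAP 7.1.7.
3. State in 7.1.7 whether lymphocyte terms are included, with the reason, given that lymphocyte reduction is a response criterion in CLL.

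If the SAP is already final, record the change in the study report, as SAP section 1 provides. The cost is an edit to a term list or to one table cell, plus a rerun of the Cytopenia AEI outputs if they have already been programmed. No new data are needed.

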7.2. Laboratory Evaluations

Laboratory data collected during the study will be analyzed and summarized using both quantitative and qualitative methods. Summaries of laboratory data in [Appendix 9](#) will be provided for the Safety Analysis Set and will include data collected up to the last dose of study drug plus 30 days for subjects who have permanently discontinued study drug. The analysis will be based on values reported in conventional units. When values are below the LOQ, they will be listed as such, and the closest imputed value will be used for the purpose of calculating summary statistics as specified in [Section 3.7](#). Hemolyzed test results will not be included in the analysis, but they will be listed in by-subject laboratory listings.

A by-subject listing for laboratory test results will be provided by subject ID number and visit in chronological order for hematology, serum chemistry, and coagulation, separately. Values falling outside of the relevant reference range and/or having a severity grade of 1 or higher on CTCAE severity grade will be flagged in the data listings, as appropriate.

No formal statistical testing is planned.

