8.6.3. Laboratory Evaluations

Safety laboratory results will be graded according to NCI-CTCAE Version 4.03. Summaries of laboratory data will be provided for the safety analysis set and will include data collected up to the last dose of study drug plus 30 days. The analysis will be based on values reported in conventional units.

Descriptive statistics will be provided by treatment groups for each safety laboratory test as follows:

- Baseline values (defined as the last measurement obtained on or prior to the date/time of first dose of study drug)
- Post baseline maximum value
- Change from baseline to post baseline maximum value
- Post baseline minimum value
- Change from baseline to post baseline minimum value

In addition, treatment-emergent laboratory abnormalities will be summarized descriptively using number and percentages of subjects by treatment group for the following:

- Grade 3 or 4 laboratory abnormalities
- Shift from baseline in laboratory toxicity grade

Subjects will be categorized according to the most severe post baseline abnormality grade for a given lab test.

CCI

CCI

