7.2.2.2. Summaries of Laboratory Abnormalities

The following summaries (number and percentage of subjects) for treatment-emergent laboratory abnormalities will be provided by lab test and treatment group; subjects will be categorized according to the most severe postbaseline abnormality grade for a given lab test:

- Graded TE laboratory abnormalities
- TE Grade 3 or 4 laboratory abnormalities

For all summaries of laboratory abnormalities, the denominator is the number of subjects with nonmissing postbaseline values up to 30 days after last dosing date.

A by-subject listing of treatment-emergent laboratory abnormalities will be provided by subject ID number and visit in chronological order. This listing will include all test results that were collected throughout the study for the lab test of interest, with all applicable severity grades and abnormal flags displayed.

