Appendix 1. Schedule of Assessments

	Screening	24 Weeks														Week 25 Day 1 ²¹	Week 29 Day 1	Every 12 weeks starting Week 33 until Week 105	EOT ¹⁹		
	Day -28	Week 1 Day 1	Week 2 Day 1	Week 3 Day 1	Week 4 Day 1 ¹⁸	Week 5 Day 1	Week 7 Day 1	Week 9 Day 1	Week 11 Day 1	Week 13 Day 1	Week 15 Day 1	Week 17 Day 1	Week 19 Day 1	Week 21 Day 1	Week 23 Day 1						
Visit Window (days)		0	±2	±2	±2	±2	±2	±2	±2	±2	±2	±2	±2	±2	±2	±7	±7	±7	±7		
Informed Consent	X																				
Medical and Medication History ¹	X																				
Physical Examination ²	X	X	X	X	X	X		X		X		X		X		X	X	X	X	X	
Vital Signs	X	X	X	X	X	X		X		X		X		X		X	X	X	X	X	
ECOG Performance Status / B-symptoms	X	X				X		X		X		X		X		X	X	X	X	X	
Binet/Rai Staging	X																				
G8 Screening Questionnaire ³		X														X		X	X	X	
12-lead ECG ⁴	X	X				X		X		X		X		X		X				X	
Adverse events/ Concomitant medications	X	X	X	X	X	X	X	X	X	X	X	X	X	X	X	X	X	X	X	X	X
Tirabrutinib + idelalisib Dispensing ⁵		X				X		X		X		X		X		X	X	X	X	X	
Tirabrutinib + idelalisib Accountability						X		X		X		X		X		X	X	X	X	X	
Obinutuzumab Administration ⁶		X	X	X		X		X		X		X		X							
Hematology ⁷	X	X	X	X	X	X	X	X	X	X	X	X	X	X	X	X	X	X	X	X	X
Chemistry ²⁰	X	X	X	X	X	X	X	X	X	X		X		X		X	X	X	X	X	

	Screening	24 Weeks														Week 25 Day 1 ²¹	Week 29 Day 1	Every 12 weeks starting Week 33 until Week 105	EOT ¹⁹	
	Day -28	Week 1 Day 1	Week 2 Day 1	Week 3 Day 1	Week 4 Day 1 ¹⁸	Week 5 Day 1	Week 7 Day 1	Week 9 Day 1	Week 11 Day 1	Week 13 Day 1	Week 15 Day 1	Week 17 Day 1	Week 19 Day 1	Week 21 Day 1	Week 23 Day 1					
Visit Window (days)		0	±2	±2	±2	±2	±2	±2	±2	±2	±2	±2	±2	±2	±2	±7	±7	±7	±7	
Coagulation (PT/INR, aPTT)	X																			X
Peripheral Blood MRD ⁸		X								X						X		X		X
Urinalysis and Urine Chemistry	X																			
Pregnancy Testing ⁹	X	X				X		X		X		X		X		X	X	X		X
Viral Serologies ¹⁰	X																			
CMV Surveillance ¹¹	X	X				X		X		X		X		X		X	X	X		
CCI																				
CCI																				
CLL phenotyping ¹⁴	X																			X
Radiographic Tumor evaluation ¹⁵	X															X				
Bone marrow evaluation ¹⁶	X															X				
Response Assessment ¹⁷						X		X		X		X		X		X	X	X		X

- 1 Medical history includes significant past medical events (eg, prior hospitalizations or surgeries), a review of the disease under study, prior anti-cancer therapies, and any concurrent medical illnesses. CIRS score should be determined at screening.

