- 14 CLL immunophenotyping, karyotyping and FISH, TP53 and IgHV mutation status, CD38 and ZAP70 expression will be evaluated from peripheral blood at screening. In the event of disease progression, only FISH and TP53 will be evaluated.
- 15 Tumor evaluation by CT scan (preferred) or MRI of neck, chest, abdomen, and pelvis will be performed at screening (unless scan was already completed up to 42 days prior to first dose). At the Week 25 visit, the same type of evaluation should be performed on those body regions which showed involvement by CLL at screening. An additional CT may be obtained on protocol per investigator discretion following evidence of an improvement in clinical response if the response assessment at the Week 25 visit is less than a complete response or in the event of suspected disease progression.
- 16 A bone marrow evaluation is required in the screening window for subjects without radiographic evidence of disease. Bone marrow aspirate and biopsy should be performed at Week 25 for subjects fulfilling clinical response criteria for CR or CRi per the modified IWCLL 2008 criteria. MRD should be assessed from bone marrow aspirate at the reference laboratory in Kiel; CCI
- CCI
- 17 Qualitative treatment response assessment based on physical exam, laboratory parameters and presence of B-symptoms should be performed every 4 weeks until Week 33 Day 1 and then at all scheduled visits thereafter following the modified IWCLL 2008 criteria, with the exception of lymphadenopathy, hepatomegaly, splenomegaly, and bone marrow. Assessment of response per modified IWCLL 2008 criteria should also be recorded at the completion of 24 weeks on treatment and subsequent to any CT and/or bone marrow biopsy that is repeated while on study.
- 18 Following evaluation of the safety data for the first 6 subjects enrolled in each treatment arm, the Safety Review Team (SRT) will determine if weekly clinical evaluation should continue for the duration of the study.
- 19 The EOT visit should be scheduled for approximately 30 days following discontinuation of all study treatment. For subjects that permanently discontinue all treatment prior to Week 25 Day 1, the Week 25 Day 1 visit should also be performed and may satisfy the requirement for the EOT visit if falling into the +30 days \pm 7 day window from all study drug discontinuation.

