Appendix 9. List of Laboratory Tests for Safety Summary

Serum Chemistry	Hematology
Sodium Potassium Chloride Glucose Blood urea nitrogen or urea Creatinine ^a ALT AST GGT Cholesterol Triglycerides Uric Acid Alkaline phosphatase Total and direct bilirubin Total protein Albumin Calcium Magnesium Phosphate LDH	WBC RBC Hemoglobin Hematocrit Platelet Count Neutrophils (ANC) Lymphocytes Monocytes Basophils Eosinophils Coagulation PT/INR aPTT

a Estimated creatinine clearance/glomerular filtration rate will be calculated based on the Cockcroft-Gault formula
 ALT = alanine aminotransferase; aPTT = activated partial thromboplastin time; AST = aspartate aminotransferase; BUN = blood urea nitrogen; GGT = gamma-glutamyltransferase; INR = international normalized ratio; LDH = lactate dehydrogenase; PT = prothrombin time; RBC = red blood cell; WBC = white blood cell

GS-US-401-1958 SAP V2.0

ELECTRONIC SIGNATURES

Signed by	Meaning of Signature	Server Date (dd-MMM- yyyy hh:mm:ss)
PPD	Clinical Research eSigned	16-Feb-2021 23:09:33
PPD	Biostatistics eSigned	19-Feb-2021 06:56:57

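### End-of-treatment PT/INR and aPTT samples taken on days 31 to 37 are inside the visit window but outside every coagulation summary table

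*SAP*

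**What the plan says.** **What is to be summarized.** SAP Appendix 9 lists "Coagulation PT/INR aPTT" alongside hematology and chemistry. SAP 7.2.1, 7.2.2 and 7.2.4 ask for baseline, post-baseline maximum and minimum, changes, graded abnormalities and shifts.

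**When it is measured.** In the schedules of both documents (Protocol Appendix 2, SAP Appendix 1), the coagulation row is marked at Screening and in the last column, EOT. No visit from Week 1 to Week 29 is marked, and neither are the 12-weekly visits to Week 105.

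**When EOT falls.** SAP Appendix 1, footnote 19: "The EOT visit should be scheduled for approximately 30 days following discontinuation of all study treatment". The EOT column carries a ±7-day window. The same footnote applies that tolerance when a Week 25 visit stands in for EOT ("7 day window from all study drug discontinuation").

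**Where the summaries stop.** SAP 7.2 "will include data collected up to the last dose of study drug plus 30 days for subjects who have permanently discontinued study drug"; Protocol 8.6.3 "will include data collected up to the last dose of study drug plus 30 days". SAP 7.2.2.1 and 7.2.4 apply the 30-day limit to treatment-emergent abnormalities and shift tables. In SAP 7.2.2.2, "the denominator is the number of subjects with nonmissing postbaseline values up to 30 days after last dosing date".

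**What is listed.** SAP 7.2 also provides by-subject listings "in chronological order for hematology, serum chemistry, and coagulation, separately", with out-of-range and graded values flagged and no 30-day limit stated.

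**The concern.** The visit window and the data cut-off were set independently, and for coagulation they collide. Hematology and chemistry have many on-treatment values, so a late EOT sample costs them little. Coagulation has one scheduled post-baseline value per subject, and the cut-off runs through the middle of the window in which it is taken. Whether a subject is counted in the PT/INR and aPTT tables then depends on whether the visit was booked for day 30 or day 31.

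This applies to 104-week completers as well as to early discontinuations, because the Week 105 visit has no coagulation test. At stake is a prespecified safety table that would rest on a subset of subjects fixed by appointment dates, with the missing ones also gone from the denominator.

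**Working it through.** The documents give no figure for this loss, so there is none to reproduce. The check is a count of days.

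**Inputs**
- EOT target: day 30 after stopping all treatment, ±7 days (SAP Appendix 1 and footnote 19).
- Cut-off: last dose + 30 days (SAP 7.2, 7.2.2.1, 7.2.2.2, 7.2.4; Protocol 8.6.3).
- Planned subjects: about 36, of whom 30 are in Arm B (SAP 1.3).
- Distribution of actual EOT days: not given, so assumed, with a range shown.

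**Step 1: permitted days.** 30 − 7 = 23 to 30 + 7 = 37, which is 15 days.

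**Step 2: split at the cut-off, with last dose and discontinuation on the same date.** Days 23 to 30 are kept: 8 of 15 = 53%. Days 31 to 37 are excluded: 7 of 15 = 47%.

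**Step 3: share excluded under different visit timings**

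| Assumed timing | Share excluded |
|---|---|
| Uniform over days 23 to 37 | 7/15 = 47% |
| Triangular, peak at day 30 (weights 8 − abs(day − 30)) | 28/64 = 44% |
| Normal around day 30, SD 3.5 days | 44% |
| Normal around day 30, SD 2 days | 40% |
| 30% of visits exactly on day 30, rest uniform over the other 14 days | 0.70 × 7/14 = 35% |
| 50% of visits exactly on day 30, rest uniform over the other 14 days | 0.50 × 7/14 = 25% |
| Uniform, discontinuation dated 1 day after last dose | 8/15 = 53% |

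The logical bounds are 0% (every visit by day 30) and 100% (every visit later).

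**Step 4: in subjects.** If every subject had an in-window EOT sample and no unscheduled test, uniform timing would exclude 36 × 7/15 = 16.8, about 17 of 36 (14 of 30 in Arm B). At 25% it would be 9 of 36, and at 53% about 19.

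**Step 5: the two clocks.** EOT is counted from discontinuation of all treatment, and the cut-off from the last dose. If discontinuation is dated *k* days after the last dose, the window becomes days 23 + *k* to 37 + *k*. Under uniform timing the excluded share is (7 + *k*)/15, reaching 15/15 at *k* = 8 (days 31 to 45). Protocol 6.5 allows interruptions of up to 2 weeks. At *k* = 14 the window is days 37 to 51. The documents do not say which date counts as discontinuation, so this step shows sensitivity and is not an estimate.

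**Step 6: after the fix.** If the EOT result is included by visit, all 15 of 15 permitted days are kept, whatever *k* is.

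**The case against.** There is a fair case for leaving the rule alone.

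- **Nothing is deleted.** A reader might infer that about half of the post-baseline coagulation results are thrown away. They are not. Late results stay in the flagged listings, which are readable with about 36 subjects. This stands, although listings give no rates, shifts or denominators.
- **Half is an assumption.** Protocol 6.7 sets EOT at 30 days to meet a 30-day safety assessment, so clustering on or before day 30, where results are kept, is plausible. This stands; hence the range.
- **Unscheduled tests count.** SAP 3.8.2 includes unscheduled visits in the maximum post-baseline grade. This stands, but none are planned.
- **The limit is a consistent convention.** It comes from Protocol 8.6.3 and matches the treatment-emergent period for adverse events. This stands, so the change must be recorded as a departure. It does not remove the conflict with the schedule.
- **A value a month after the last dose says little about on-treatment coagulation.** This is true of day 29 and day 34 alike, and so is no reason to separate them.

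Two stronger readings are tempting and unsupported. The first is that subjects stopped after a toxicity interruption are always lost. That needs a gap of at least 8 days and a discontinuation date later than the last dose. The date is undefined, and SAP 7.1.5.1 and 7.1.5.2 count the same 30 days from permanent discontinuation and from last dose respectively. Stopping one drug also does not trigger EOT. The second is that the bleeding assessment is weakened. SAP 7.1.7 counts hemorrhage from reported adverse events. The aPTT and INR entries in Appendix 4 are adverse event terms, and Protocol 7.1.3 has laboratory abnormalities that need intervention or change dosing reported as adverse events. The laboratory cut-off alters none of those counts.

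**Conclusion.** The mismatch is real and minor. EOT coagulation results from days 31 to 37 comply with the schedule but fall out of every coagulation summary, abnormality and shift table. A subject without an unscheduled test also leaves the denominator. That is 7 of 15 permitted days.

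As a share of results it is 47% if visits are uniform and about 25% to 53% across the timings tried. It could be larger if discontinuation is dated after the last dose. These shares rest on assumed visit timing, and the subject counts also assume that every subject has an in-window EOT sample. The documents support neither a fixed figure of one half nor a claim of selective loss.

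The consequence is confined to descriptive safety tables. The primary endpoint and the hemorrhage adverse event counts are unaffected.

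**What to change.** Add to SAP 7.2, with cross-references in 7.2.2.1, 7.2.2.2 and 7.2.4:

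*For PT/INR and aPTT, the result from the scheduled EOT visit is included in the numeric summaries, abnormality tables and their denominators, and shift tables, irrespective of the 30-day limit.*

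Footnote those tables to say that scheduled post-baseline values were taken off treatment and that some fall after day 30. Record the change from Protocol 8.6.3 in SAP 7.7, which now reports no deviations. If the SAP is already final, SAP Section 1 provides for documenting the change in the CSR.

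Tying inclusion to the visit, and not to last dose + 37 days, avoids having to settle the discontinuation date. Hematology and chemistry can keep the present limit.

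The cost is a few lines of text and a programming exception for two tests, with no new data. The downside is that some coagulation values from outside the 30-day treatment-emergent period used elsewhere enter the tables, which the footnote discloses. The change does not supply on-treatment coagulation data. That would need extra sampling under a protocol change and is not proposed here.
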